4.1.1. Phase 1: Dose Escalation of INCB001158 + Epacadostat + Pembrolizumab

In this study, the RP2D of both the triplet (INCB001158 + epacadostat + pembrolizumab) and doublet (INCB001158 + epacadostat) will be determined from the dose escalation of the triplet combination in Phase 1. The INCB001158 dose will be escalated while keeping the epacadostat (100 mg BID) and pembrolizumab (200 mg Q3W) doses fixed at the levels used to study this doublet in Phase 3 (NCT02752074; eIB). INCB001158 is not expected to have overlapping toxicity with either of these molecules, based on their respective mechanisms and on the available safety data from the first-in-human study, INCB 01158-101 (iIB), and the epacadostat + pembrolizumab INCB 24360-202 Phase 2 study (Hamid et al 2017a). In the ongoing INCB 01158-101 study, INCB001158 doses have been identified that are pharmacologically active and well-tolerated (Papadopoulos et al 2017). Thus, it is hypothesized that when INCB001158 is escalated with the Phase 3 doses of epacadostat plus pembrolizumab, an RP2D will be identified based on an INCB001158 PAD and before an MTD is reached. In that case, the INCB001158 and epacadostat doses in the triplet RP2D would be appropriate to also use as the RP2D for the INCB001158 + epacadostat doublet in Phase 2 Part B. Hence, no separate dose escalation of INCB001158 with epacadostat 100 mg BID will be conducted in this study.

An open-label, BOIN design (Liu and Yuan 2015) will be used to determine the RP2D of the triplet combination of INCB001158, epacadostat, and pembrolizumab in 21-day treatment cycles in subjects with advanced or metastatic solid tumors. Given the target DLT rate of 33% for the

INCB001158 plus epacadostat and pembrolizumab combination, the dose escalation and de-escalation rules are shown in [Table 2](#). The BOIN design also includes an elimination rule. When ≥ 3 subjects have been treated, if the probability that the estimated toxicity rate that is above the target DLT rate is $> 95\%$ at a certain dose level, then this dose level and higher dose levels are assumed too toxic and will be eliminated. If the lowest dose level is eliminated, the whole dose escalation will be terminated. [Table 2](#) (in the bottom row) provides the elimination rules. Based on this algorithm, a minimum of 3 evaluable subjects and a maximum of 9 evaluable subjects will be enrolled at each tested dose level. The dose escalation will continue, based on the rules in [Table 2](#), until the rules require at least 1 of the following:

- Enrollment of additional subjects in a cohort that already has 9 evaluable subjects, or
- Dose escalation to a dose level that has already been eliminated, or
- Dose escalation above the maximum allowable dose level identified in the INCB 01158-101 study (see [Section 1.2.4](#)).

At that point, the dose escalation will be stopped.

Table 2: Dose Escalation, De-Escalation, and Elimination Boundaries for Target DLT Rate = 33% in Phase 1

Action	The Number of Subjects Treated at the Current Dose								
	1	2	3	4	5	6	7	8	9 ^a
Escalate if # of DLTs \leq	NA	NA	0	1	1	1	1	2	2
De-escalate if # of DLTs \geq	1	1	2	2	2	3	3	4	4
Elimination if # of DLTs \geq	NA	NA	3	3	4	4	5	5	6

DLT = dose-limiting toxicity; NA = not applicable.

^a If 9 evaluable subjects are enrolled in a cohort and 3 of those subjects experience a DLT, then the medical monitor and the investigators will review the entirety of the data and decide whether to dose-escalate, dose-de-escalate, or to stop at that dose level.

Dose escalation will begin with starting doses of INCB001158 at least 2 dose levels below the maximum tolerated and tested dose from the INCB 01158-101 study (likely to be 50 mg BID or 75 mg BID – see [Table 3](#) and [Table 4](#), respectively). If the starting dose is not one of those 2 dose levels, then a revised dose escalation table will be provided to sites. However, the starting doses of epacadostat (100 mg PO BID continuous dose administration) and pembrolizumab (200 mg IV Q3W) will not be changed. Epacadostat 100 mg BID was selected as the starting dose because it has been shown to be active and tolerable in several epacadostat combination clinical studies, including with pembrolizumab ([eIB](#), [Gangadhar et al 2017](#), [Hamid et al 2017a](#), [Hamid et al 2017b](#), [Smith et al 2017](#)). The starting dose of pembrolizumab is the standard, approved dose and schedule ([Keytruda PI](#), [Keytruda SPC](#)) and also the dose used in combination with epacadostat in Phase 3.

If the starting doses of the triplet combination of INCB001158, epacadostat, and pembrolizumab are tolerable (eg, none of the first 3 evaluable subjects experiences a DLT; see [Section 5.4.2](#)),

then the INCB001158 dose will be escalated in subsequent cohorts, while keeping the epacadostat and pembrolizumab doses constant, until one of the stopping rules (described above and in [Table 2](#)) is met.

If the starting doses of INCB001158, epacadostat 100 mg BID, and pembrolizumab 200 mg Q3W are not tolerable, then an additional cohort will be enrolled at a reduced dose of either INCB001158 or epacadostat, depending on which one is deemed most likely to have caused the intolerability, upon agreement between the medical monitor and the study investigators (ie, Dose Level -1A or -1B; see [Table 3](#) and [Table 4](#)).

A PAD will be defined as a dose at or below the monotherapy MTD at which at least half of the subjects (and at least 2 subjects in total) enrolled at a particular dose level achieve a trough (C_{\min}) plasma concentration of INCB001158 at steady state of $\geq 1 \mu\text{M}$, which is equivalent to the IC_{90} for arginase 1. This definition may be modified based on emerging data from the INCB 01158-101 first-in-human study, upon agreement between the medical monitor and the study investigators. The MTD, if reached, is the maximum tested dose of INCB001158, such that no more than 33% of the subjects receiving the triplet combination experience a DLT during the first 6 weeks on study drug.

Dose interruptions and/or modifications may be implemented based on toxicity. Dose modifications should not be made during the DLT observation period without discussion with the medical monitor. Intrasubject dose escalation is not permitted.

After completing the dose escalation per the BOIN rules, one of the INCB001158 dose levels that is pharmacologically active (ie, a PAD) and tolerable in combination with epacadostat 100 mg BID or lower and pembrolizumab 200 mg Q3W (ie, MTD or lower) will be selected, and that triplet combination will be the RP2D. The doublet RP2D would consist of the same doses of INCB001158 and epacadostat.

Note that if a dose level to be assigned as RP2D has fewer than 9 evaluable subjects in it, then the medical monitor and study investigators can consider adding subjects to a total of 9 before making the final RP2D decision.

The safety and tolerability of the triplet RP2D will be further assessed in 9 tumor expansion cohorts in Phase 2 Part A (see [Section 4.1.2](#)), and the safety and tolerability of the doublet RP2D will be further assessed in 3 tumor expansion cohorts in Phase 2 Part B (see [Section 4.1.3](#)).

Telephone conferences will be scheduled by the sponsor with study investigators in order to review cohort-specific data and overall safety data, agree on dose escalation/de-escalation, adjudicate individual high-grade AEs as potentially dose-limiting, and guide other major study decisions.

Table 3: Dose Levels for Phase 1: INCB001158 + Epacadostat + Pembrolizumab, Based on INCB001158 Starting Dose of 50 mg BID

Dose Level	INCB001158	Epacadostat	Pembrolizumab
-1B ^a	50 mg PO BID	50 mg PO BID	200 mg IV Q3W
-1A ^b	25 mg PO BID	100 mg PO BID	200 mg IV Q3W
1	50 mg PO BID	100 mg PO BID	200 mg IV Q3W
2	75 mg PO BID	100 mg PO BID	200 mg IV Q3W
3	100 mg PO BID	100 mg PO BID	200 mg IV Q3W
4	150 mg PO BID	100 mg PO BID	200 mg IV Q3W

^a -1 dose level to be used if unacceptable toxicity is observed at Dose Level 1 and is deemed to be due to epacadostat.

^b -1 dose level to be used if unacceptable toxicity is observed at Dose Level 1 and is deemed to be due to INCB001158.

Table 4: Dose Levels for Phase 1: INCB001158 + Epacadostat + Pembrolizumab, Based on INCB001158 Starting Dose of 75 mg BID

Dose Level	INCB001158	Epacadostat	Pembrolizumab
-1B ^a	75 mg PO BID	50 mg PO BID	200 mg IV Q3W
-1A ^b	50 mg PO BID	100 mg PO BID	200 mg IV Q3W
1	75 mg PO BID	100 mg PO BID	200 mg IV Q3W
2	100 mg PO BID	100 mg PO BID	200 mg IV Q3W
3	150 mg PO BID	100 mg PO BID	200 mg IV Q3W

^a -1 dose level to be used if unacceptable toxicity is observed at Dose Level 1 and is deemed to be due to epacadostat.

^b -1 dose level to be used if unacceptable toxicity is observed at Dose Level 1 and is deemed to be due to INCB001158.

At the discretion of the sponsor, up to a total of 6 additional "backfill" subjects may be enrolled at any tolerable dose level to further investigate safety [REDACTED].

[REDACTED]

4.1.2. Phase 2 Part A: Tumor Expansion of INCB001158 + Epacadostat + Pembrolizumab

The RP2D of the triplet combination of INCB001158, epacadostat, and pembrolizumab identified in Phase 1 will be further assessed in Phase 2 Part A in the following 9 tumor expansion cohorts, 5 of which include only anti-PD-1/PD-L1-naïve subjects, and 4 of which include only subjects who have received an anti-PD-1 or anti-PD-L1 agent in a recent line of therapy:

- Cohort A1: Subjects with anti-PD-1/PD-L1-naïve NSCLC who have received no more than 2 prior systemic chemotherapy regimens for Stage IV disease, one of which must include a platinum-based therapy (see Inclusion Criterion 3 for more details). In a similar population in the INCB 24360-202 study, the ORR for epacadostat + pembrolizumab was 39% ([Gangadhar et al 2017](#)). However, in this study, a slightly lower ORR of 30% will be used as the background ORR.
- Cohort A2: Subjects with locally advanced unresectable or metastatic NSCLC who received prior treatment with anti-PD-1 or anti-PD-L1 therapy (alone or as part of a combination) in the advanced or metastatic setting and have PD as their best response to treatment that is confirmed at least 4 weeks later (see Inclusion Criterion 4 for more details). This population is expected to be refractory to further anti-PD-1/anti-PD-L1 treatment. This will be known as the primary anti-PD-1/anti-PD-L1 refractory cohort (primary refractory).
- Cohort A3: Subjects with locally advanced unresectable or metastatic NSCLC who have received prior anti-PD-1 or anti-PD-L1 therapy (alone or as part of a combination) in the advanced or metastatic setting and achieved either SD for at least 24 weeks or PR/CR but later have confirmed PD (PD confirmed at least 4 weeks later). See Inclusion Criterion 5 for more details. This will be known as the anti-PD-1/PD-L1-relapsed cohort (relapsed).
- Cohort B1: Subjects with anti-PD-1/PD-L1-naïve melanoma who have received no more than 2 prior lines of systemic therapy for unresectable Stage III or Stage IV disease (see Inclusion Criterion 6 for more details). In a similar population in the INCB 24360-202 study, the ORR for epacadostat + pembrolizumab was 56% ([Gangadhar et al 2016](#)).
- Cohort B2: Subjects with unresectable Stage III or Stage IV melanoma who received prior treatment with anti-PD-1 or anti-PD-L1 therapy (alone or as part of a combination) in the advanced or metastatic setting and have PD as their best response to treatment that is confirmed at least 4 weeks later (see Inclusion Criterion 7 for more details). This population is expected to be refractory to further anti-PD-1/anti-PD-L1 treatment. This will be known as the primary anti-PD-1/PD-L1-refractory cohort (primary refractory).

- Cohort B3: Subjects with unresectable Stage III or Stage IV melanoma who have received prior anti-PD-1 or anti-PD-L1 therapy (alone or as part of a combination) in the advanced or metastatic setting and achieved either SD for at least 24 weeks or PR/CR, but later have confirmed PD (PD confirmed at least 4 weeks later). See Inclusion Criterion 8 for more details. This will be known as the anti-PD-1/PD-L1-relapsed cohort (relapsed).
- Cohort C: Subjects with PD(L)1-naive urothelial carcinoma who have received no more than 2 prior lines of systemic chemotherapy regimens for metastatic or inoperable locally advanced disease, one of which must include a platinum-based therapy (see Inclusion Criterion 7 for more details). In a similar population in the INCB 24360-202 study, the ORR for epacadostat + pembrolizumab was 38% (first and second line) and 25% (third line and beyond; [Smith et al 2017](#)).
- Cohort D: Subjects with PD(L)1-naive SCCHN not amenable to local therapy with curative intent, who have received at least 1 prior platinum-based systemic chemotherapy regimen, and no more than 2 prior systemic chemotherapy regimens (see Inclusion Criterion 8 for more details). In a similar population in the INCB 24360-202 study, the ORR for epacadostat + pembrolizumab was 39% ([Hamid et al 2017b](#)).
- Cohort E: Subjects with PD(L)1-naive, advanced or metastatic SCLC who have received at least 1 line of therapy that includes a platinum-based regimen in the first-line setting, and no more than 2 prior lines of chemotherapy (see Inclusion Criterion 9 for more details). In a broadly similar PD-L1-unselected population in the CheckMate 032 study, the ORR for nivolumab was 11%, whereas the ORR in a PD-L1-positive population treated with pembrolizumab was 33% ([Hellman et al 2017](#), [Ott et al 2016](#); see also Section 1.2.3.2). However, the sample sizes were small in each study, so these differences in ORR observed with pembrolizumab and nivolumab may not pan out in larger studies. For the purposes of this study, the baseline ORR was selected based on the average ORR of the 2 anti-PD-1 agents and allowing for some theoretical additive activity from epacadostat. Of note, epacadostat has not been studied in combination with an anti-PD-1 agent.

In each cohort, the ORR of the triplet combination will be assessed using a Simon 2-stage design (see [Table 5](#)), to determine whether the combination has sufficient antitumor activity to warrant further testing in subsequent clinical studies. The basis for the background ORR selected for each cohort is described above.

Note that the sponsor may evaluate fewer expansion cohorts or some cohorts in sequence, at their discretion.

If, at the time of completion of enrollment in Stage 1, it is not known whether the target ORR to proceed to Stage 2 will be met, then enrollment will be paused until and unless the ORR to proceed has been met.

Table 5: Phase 2 Part A: Simon 2-Stage Design

Cohort	Background ORR	Target ORR	Alpha	Power	N for Stage 1	ORR to Proceed $\geq (r_1 + 1) / n_1^a$	N for Stage 2	ORR for Positive Cohort $\geq (r + 1) / n^a$
A1	30%	50%	0.1	80%	15	6/15	17	13/32
A2	2%	15%	0.1	80%	11	1/11	15	2/26
A3	15%	35%	0.1	80%	9	2/9	14	6/23
B1	56%	76%	0.1	80%	12	8/12	19	21/31
B2	2%	15%	0.1	80%	11	1/11	15	2/26
B3	15%	35%	0.1	80%	9	2/9	14	6/23
C	30%	50%	0.1	80%	15	6/15	17	13/32
D	39%	59%	0.1	80%	15	7/15	16	16/31
E	25%	45%	0.1	80%	15	5/15	12	10/27

^a r_1 = response rate at the end of Stage 1; n_1 = sample size for Stage 1 only; r = overall response rate for combined Stage 1 and 2; n = sample size for combined Stage 1 and 2.

4.1.3. Phase 2 Part B: Tumor Expansion of INCB001158 + Epcadostat

The RP2D of INCB001158 and epcadostat identified in Phase 1 will be assessed in Phase 2 Part B, in the following 3 tumor expansion cohorts:

- Cohort A: Subjects with metastatic or inoperable locally advanced urothelial carcinoma who have had disease progression on prior standard therapy with a platinum-based regimen and a checkpoint inhibitor (see Inclusion Criterion 12 for more details).
- Cohort B: Subjects with metastatic or recurrent SCCHN not amenable to local therapy with curative intent, who had disease progression on prior treatment with a platinum-based therapy and an anti-PD-1 therapy (see Inclusion Criterion 13 for more details).
- Cohort C: Subjects with CRC who have failed prior standard therapy (see Inclusion Criterion 14 for more details).

In each cohort, the ORR of the doublet combination will be assessed using a Simon 2-stage design (see Table 6), to determine whether the combination has sufficient antitumor activity to warrant further testing in subsequent clinical studies. Neither study drug has demonstrated antitumor activity as monotherapy in patients with advanced or metastatic cancer (refer to iIB and eIB), so the assumed background ORR of 2% is based on the doublet also not having antitumor activity. The target ORR of 15% represents an active doublet.

If, at the time of completion of enrollment in Stage 1, it is not known whether the target ORR to proceed to Stage 2 will be met, then enrollment will be paused until and unless the ORR to proceed has been met.

Table 6: Phase 2 Part B: Simon 2-Stage Design

Cohort	Background ORR	Target ORR	Alpha	Power	N for Stage 1	ORR to Proceed $\geq (r1 + 1) / n1^a$	N for Stage 2	ORR for Positive Cohort $\geq (r + 1) / n^a$
A	2%	15%	0.1	80%	11	1/11	15	2/26
B	2%	15%	0.1	80%	11	1/11	15	2/26
C	2%	15%	0.1	80%	11	1/11	15	2/26

^a r1 = response rate at the end of Stage 1; n1 = sample size for Stage 1 only; r = overall response rate for combined Stage 1 and 2; n = sample size for combined Stage 1 and 2.

4.2. Measures Taken to Avoid Bias

This is an open-label study; no comparisons will be made between subjects. Measurements of safety and efficacy are objective measurements, and only comparisons to pretreatment conditions will be made.

4.3. Number of Subjects

4.3.1. Planned Number of Subjects

Under Protocol Amendment 2, up to 5 subjects will be enrolled in the dose-escalation (Phase 1) part. No subjects will be enrolled in Phase 2.

It is planned to have 4 sites during Phase 1.

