Safety follow-up: 30 to 37 days after last dose of INCB001158 and epacadostat (all subjects); 90 to 97 days after last dose of INCB001158 and epacadostat (Phase 1 and Phase 2 Part A only).

[REDACTED]

Estimated Duration of Participation: In the triplet combination (INCB001158 + epacadostat + pembrolizumab) Phase 1 and Phase 2 Part A, subjects may continue on treatment for as long as they are receiving benefit and do not meet withdrawal criteria, for up to 35 cycles (approximately 2 years). In the doublet combination (INCB001158 + epacadostat) Phase 2 Part B, subjects may continue on treatment for as long as they are receiving benefit and do not meet withdrawal criteria.

Estimated Number of Subjects: With Protocol Amendment 2, up to 5 subjects will be enrolled in the dose-escalation (Phase 1), and no subjects will be enrolled in Phase 2.

Principal Coordinating Investigator: TBD

Statistical Methods:

Given that enrollment was terminated (Amendment 2) during the Phase 1 portion of the study, all efficacy analyses will now be only exploratory, and some planned tables and figures may be replaced with listings.

Sample Size Method: In Phase 1, a BOIN design will be used to determine the RP2D of the triplet combination of INCB001158, epacadostat, and pembrolizumab in 21-day treatment cycles in subjects

with advanced or metastatic solid tumors. The RP2D will then be further assessed in triplet tumor expansion cohorts in Phase 2 Part A. The equivalent INCB001158 + epacadostat doublet RP2D will be further assessed in doublet tumor expansion cohorts in Phase 2 Part B.

Each Simon 2-stage design will have a stopping rule to allow early termination of a particular tumor type within a treatment group at the end of Stage 1 if there is insufficient response observed, while enrolling enough subjects to predict possible target responses worthy of cohort expansion and potential further evaluation in future studies.

The proposed designs for each tumor type will be used for any planned Simon 2-stage design. Each Simon 2-stage design is set up to have a 1-sided Type I error of 0.1 and power of 80%. The response rates for each tumor type will be estimated with 95% confidence intervals.

Phase 2 Part A: Simon 2-Stage Design

Cohort	Background ORR	Target ORR	Alpha	Power	N for Stage 1	ORR to Proceed $\geq (r_1 + 1) / n_1^a$	N for Stage 2	ORR for Positive Cohort $\geq (r + 1) / n^a$
A1	30%	50%	0.1	80%	15	6/15	17	13/32
A2	2%	15%	0.1	80%	11	1/11	15	2/26

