2. STUDY OBJECTIVES AND ENDPOINTS

The study objectives and endpoints are presented in [Table 1](#).

Table 1: Study Objectives and Endpoints

Objectives	Endpoints
Primary	
Phase 1 only: To assess the safety and tolerability, and to determine the RP2D of INCB001158 in combination with epacadostat ± pembrolizumab.	Safety, tolerability, DLTs, and RP2D of INCB001158 in combination with epacadostat ± pembrolizumab, as assessed by AEs, clinical laboratory assessments, physical examination results, and 12-lead ECG results.
Phase 2 only: To evaluate the ORR of INCB001158 in combination with epacadostat ± pembrolizumab.	ORR, defined as the percentage of subjects having a CR or PR, as determined by investigator assessment of radiographic disease as per RECIST v1.1.
Secondary	
Phase 2 only: To assess the safety, tolerability, and RP2D of INCB001158 in combination with epacadostat ± pembrolizumab.	Safety, tolerability, and RP2D of INCB001158 in combination with epacadostat ± pembrolizumab, as assessed by AEs, clinical laboratory assessments, physical examination results, and 12-lead ECG results.
To evaluate the antitumor effect of INCB001158 in combination with epacadostat ± pembrolizumab by RECIST v1.1.	
 • ORR, defined as the percentage of subjects having a CR or PR, as determined by investigator assessment of radiographic disease as per RECIST v1.1 (Phase 1 only). • DCR, defined as the percentage of subjects having CR, PR, or SD for at least 56 days, as determined by investigator assessment of radiographic disease as per RECIST v1.1. • DoR, determined by radiographic disease assessment, defined as the time from earliest date of disease response until the earliest date of disease progression per RECIST v1.1, or death due to any cause, if occurring sooner than progression. • PFS, defined as the time from date of first dose of study treatment until the earliest date of disease progression, as determined by investigator assessment of objective radiographic disease assessments per RECIST v1.1, or death due to any cause, if occurring sooner than progression.
To determine the PK of each of INCB001158 and epacadostat in subjects treated with INCB001158 in combination with epacadostat ± pembrolizumab.	The PK of INCB001158 and epacadostat will be assessed by summarizing C_{max} , t_{max} , C_{min} , AUC_{0-t} , and Cl/F .

Table 1: Study Objectives and Endpoints (Continued)

Objectives	Endpoints
[Redacted Content]	

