9.2. Selection of Sample Size

9.2.1. Sample Size for Phase 1

In Phase 1, the BOIN design will be used to determine the RP2D of the combination of INCB001158, epacadostat, and pembrolizumab, in 21-day treatment cycles in subjects with advanced or metastatic solid tumors. The details of the dose escalation, de-escalation, and elimination boundaries according to the BOIN design are provided in Section 4.1.1.

9.2.2. Sample Size for Phase 2

Phase 2 will further evaluate the safety, tolerability, preliminary efficacy, PK, and pharmacologic activity of the recommended dose of INCB001158 in combination with epacadostat \pm pembrolizumab, as part of dose expansion cohorts in Part A (INCB001158 plus epacadostat and pembrolizumab) and Part B (INCB001158 and epacadostat). In Phase 2, a Simon 2-stage design will be run for each tumor type within a given treatment group.

The sample size for each tumor type within a given treatment group will be guided by the Simon 2-stage design. The planned Simon 2-stage designs are summarized in Table 5 and Table 6. Each Simon 2-stage design will have a stopping rule to allow early termination of a particular tumor type within the given treatment group at the end of Stage 1 if there is insufficient response observed, while enrolling enough subjects to predict possible target responses worthy of cohort expansion and potential further evaluation in future studies. The individual Simon 2-stage designs run for each tumor type within each treatment group will have design parameters that are determined by historical response rates.

In order to determine whether the target response rate ($p_1\%$) is likely, an initial number of evaluable subjects (n_1 subjects) will be treated at the RP2D of INCB001158 in combination with

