9.5. Interim Analysis

9.5.1. Interim Analysis for the BOIN Design

In Phase 1, the BOIN design will be used to determine the RP2D of the combination of INCB001158, epacadostat, and pembrolizumab. For the design parameters, let δ denote the target DLT rate, δ_1 denote the highest toxicity probability below the MTD so that dose escalation is required, and δ_2 denote the lowest toxicity probability deemed overly toxic so that dose de-escalation is required. We assume that $\delta_1 = 0.6 \delta$ and $\delta_2 = 1.4 \delta$. Also, to avoid assigning too many subjects to an overly toxic dose, we use the dose elimination rule when implementing the BOIN design. If $p_r(p_j > \delta | m_j, n_j) > 0.95$ and $n_j \geq 3$, dose levels j and higher are eliminated from the study, and the dose escalation is terminated if the lowest dose level is eliminated, where p_j represents the toxicity rate, δ represents the target DLT rate, n_j represents the total subjects who have been treated, and m_j represents the subjects who have experienced toxicity at dose level j . Section 4.1.1 Table 2 (in the bottom row) provides the elimination boundaries for the target DLT rate of 33%. For example, when the number of subjects treated at the current dose $n_j = 4$, we will eliminate that dose and higher doses if 3 or more subjects experience toxicity.

Based on the algorithm of the BOIN design, a minimum of 3 evaluable subjects will be enrolled in each dose level with a maximum of 9 evaluable subjects in each dose level.

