APPENDIX D. PROTOCOL AMENDMENT SUMMARY OF CHANGES

DOCUMENT HISTORY	
Document	Date
Amendment (Version) 1:	27 OCT 2017
Amendment (Version) 2:	01 JUN 2018

Amendment 2 (Version 2 dated 01 JUN 2018)

The main reason for the Amendment is to halt enrollment into the study, based on emergent data from the ECHO-301/KEYNOTE-252 melanoma clinical study in which an interim analysis revealed that the study did not meet the prespecified endpoint of improvement in progression-free survival for the combination of pembrolizumab and epacadostat compared with pembrolizumab and placebo ([Long et al 2018](#)).

In addition, this amendment includes some corrected errors and a few updates based on new information (updated epacadostat safety information and the defined INCB001158 starting dose).

This amendment includes the changes to the Protocol INCB 01158-202 Amendment (Version) 1 (27 OCT 2017) summarized below.

1. Synopsis; Section 4.3, Number of Subjects

Description of change: The estimated number of subjects to be enrolled and number of study sites in this study has been updated.

Rationale for change: The early termination of enrollment will limit the number of subjects to be enrolled.

2. Synopsis; Section 4.6.1, Protocol Amendment 2

Description of change: All further enrollment into this study was halted. Subjects who have consented and are in screening as of 08 MAY 2018 are permitted to enroll if eligibility is determined per Section 3, and subjects currently on treatment may continue as long as they are deriving clinical benefit, tolerating the treatment, and do not meet any withdrawal criteria. Phase 1 backfill cohorts and Phase 2 will not be opened.

Rationale for change: The premise of this study was based on epacadostat + pembrolizumab having greater antitumor activity than pembrolizumab alone. However, because the ECHO-301/KEYNOTE-252 melanoma clinical study did not meet the prespecified endpoint of improvement in progression-free survival for the combination of pembrolizumab + epacadostat compared with pembrolizumab + placebo, it was decided to close all further enrollment into the INCB 01158-202 study.

3. **Synopsis; Section 9, Statistics**

Description of change: All efficacy analyses will now only be exploratory; some planned tables and figures may be replaced by listings.

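### Does a Phase 1 limit of 5 subjects leave the recommended-dose objective and the PK analysis without a workable plan?

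*Combined protocol and SAP*

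**What the plan says.** Amendment 2 halts enrolment. The synopsis states that "up to 5 subjects will be enrolled in the dose-escalation (Phase 1), and no subjects will be enrolled in Phase 2", and Section 4.3.1 repeats the Phase 1 figure: "up to 5 subjects will be enrolled in the dose-escalation (Phase 1) part". The log in Appendix D describes the edit this way: "The estimated number of subjects to be enrolled and number of study sites in this study has been updated". Section 9 makes the efficacy analyses exploratory and lets listings replace some outputs. Section 4.6.1 tells readers to disregard text on parts of the study that will not be run.

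The dose-finding text was not revised to match:

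- Table 1 keeps the primary objective: "Phase 1 only: To assess the safety and tolerability, and to determine the RP2D of INCB001158".
- Section 4.1.1 requires "a minimum of 3 evaluable subjects and a maximum of 9 evaluable subjects will be enrolled at each tested dose level" and gives three conditions that end escalation. Selection comes next: "After completing the dose escalation per the BOIN rules, one of the INCB001158 dose levels that is pharmacologically active".
- Section 9.2.1 still says "the BOIN design will be used to determine the RP2D of the combination", and Section 9.5.1 adds: "Based on the algorithm of the BOIN design, a minimum of 3 evaluable subjects will be enrolled in each dose level".

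On PK, Section 9.4.3 restricts the non-compartmental parameters to the first twelve subjects of Phase 2 Part B and plans population PK for everyone. Section 7.9.1 gives those twelve extensive sampling and all other subjects sparse sampling. The synopsis includes AUC over the dosing interval among the PK endpoints; Table 1 has Cl/F in its place.

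**The concern.** The amendment reclassified efficacy but said nothing about the RP2D. With at least 3 evaluable subjects per tested level, 5 subjects cannot fill two levels, so the primary objective appears to promise something the design can no longer deliver. The fear is that the final report either leaves part of its primary objective unanswered without a prespecified statement, or names a dose that the BOIN rules never reached.

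The PK secondary objective carries no Phase 2 label, so it covers Phase 1. Its parameters match those that Section 9.4.3 derives by non-compartmental methods from Part B subjects, of whom there will be none. Section 4.3.2 also still calls for enrolment until 3 subjects are evaluable, which sits badly with a halt.

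**Working it through.** **1. Reproduce Table 2.** Section 9.5.1 gives a target of 0.33 and interval limits of 0.6 and 1.4 times the target, so p1 = 0.198 and p2 = 0.462.

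- Escalation boundary: ln[(1 − 0.198)/(1 − 0.33)] / ln[0.33(1 − 0.198)/(0.198(1 − 0.33))] = 0.2604.
- De-escalation boundary: ln[(1 − 0.33)/(1 − 0.462)] / ln[0.462(1 − 0.33)/(0.33(1 − 0.462))] = 0.3947.
- At n = 3: 3 × 0.2604 = 0.78, so escalate at 0; 3 × 0.3947 = 1.18, so de-escalate at 2 or more.
- At n = 9: 2.34 gives 2, and 3.55 gives 4.
- Elimination, with a Beta(1,1) prior (assumed, since none is named): 3/3 gives 1 − 0.33⁴ = 0.988, above 0.95.

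Every Table 2 entry reproduces. The NA cells at n = 1 and 2 follow from the 3-subject minimum.

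**2. Fewest evaluable subjects at each stop that leaves a selectable dose.**

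| Stop condition (Section 4.1.1) | What it needs | Minimum |
|---|---|---|
| Escalation into an eliminated level | 3 at the eliminated level (3/3) + 3 at the level below (0/3) | 6 |
| Cohort already full | 9 at one level | 9 |
| Escalation above the maximum, starting at 75 mg (Table 4) | 3 levels × 3 | 9 |
| Escalation above the maximum, starting at 50 mg (Table 3) | 4 levels × 3 | 12 |

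A route through a −1 level also needs 3 + 3 = 6. Escalation that ends because the lowest level is eliminated leaves nothing to select.

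**3. Compare with the limit.**

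- *5 is the total.* The shortfall is 6 − 5 = 1 at best, and 9 − 5 = 4 or 12 − 5 = 7 with no DLTs. The probability of completing with a selectable dose is 0 whatever the DLT rates.
- *5 is in addition to subjects already treated.* If all 5 are evaluable, completion needs at least 1 earlier evaluable subject on the fastest path, and 4 or 7 with no DLTs. The number already treated is not given. With exactly 6 evaluable subjects in cohorts of 3, and DLT probabilities q, a and b at levels −1, 1 and 2, the completion probability is (1 − a)³b³ + a³(1 − q)³. With 10% throughout, this is 0.729 × 0.001 + 0.001 × 0.729 = 0.0015. With q = 0.10, a = 0.20 and b = 0.50, it is 0.512 × 0.125 + 0.008 × 0.729 = 0.0698. These rates are assumptions.

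**4. What the text yields if escalation does not complete.** Selection is conditional on completion, and Section 4.1.1 defines the MTD only for the case in which it is reached. No provision allows a dose to be named otherwise. The outcome is therefore fixed: no RP2D. Section 9.1 still defines the DLT evaluable population and the full analysis set, so DLTs by dose level and the safety tables are unaffected.

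**5. PK.**

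| | Extensive sampling, non-compartmental | Sparse sampling, population PK |
|---|---|---|
| Who, as planned | First 12 in Part B | Population PK for all; sparse sampling for all others, including Phase 1 |
| After Amendment 2 | 0 | The Phase 1 subjects |

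Non-compartmental analysis was never intended for Phase 1. The zero comes from Part B not opening, whatever the Phase 1 number is, and the instruction in Section 4.6.1 covers that text. Steady-state trough concentration in Phase 1 is already needed for the definition of a pharmacologically active dose in Section 4.1.1.

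**The case for a change.** The strongest argument for a change is that the instruction to disregard text reaches only parts that will not be run. Phase 1 is described as ongoing, and subjects in screening may still enter, so Table 1 and Sections 4.1.1, 9.2.1 and 9.5.1 remain in force. Section 9 and the log deal only with efficacy. A few sentences would remove any doubt at no cost in subjects or samples. On PK, disregarding the Part B sentence removes a derivation without saying which listed parameters population PK will supply, and the two endpoint lists differ.

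Much of this stands as description. The RP2D component was not restated, the limit of 5 can be read two ways, and the PK lists do not match. What does not stand is the harm. The sections that remain in force include the one that forbids selection before completion, so leaving them in force prevents an off-rule dose. An objective unmet because a study was openly stopped is a consequence of termination, not an analysis error.

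As to which PK parameters will be reported, the public copy does not show the sparse sampling times, and Appendix B leaves further detail to the statistical analysis plan, so a gap cannot be established. The replacement wording in Sections 4.3.2 and 5.4.2 gives way to the explicit halt in Section 4.6.1.

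**Conclusion.** The arithmetic is right: at least 6 evaluable subjects are needed against a limit of 5, if 5 is the total. The synopsis heading and the log favour that reading but do not settle it. The conclusion does not depend on the reading, because the same rule governs both cases: an RP2D if escalation completes, none if it does not. An analyst following Sections 4.1.1, 5.4.2 and 9.1 would report DLTs as counts over evaluable subjects at each dose level, report safety in full, and declare no RP2D from an incomplete escalation. A rewritten objective would say the same.

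On PK, the analysis designed for Phase 1 is intact, and the difference between AUC over the dosing interval and Cl/F is a clerical mismatch between two lists. This is a gap in wording that analysts fill sensibly in a terminated study. No estimate, error rate, subject-level decision or later part of the study changes, so no amendment is warranted.
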